## Ethical approval

As participants will be recruited outside of the NHS, ethics approval will be sought from the University of East Anglia's Faculty of Medicine and Health's Research Ethics Committee.

#### Intervention group

Participants randomised into this arm will gain access to the online fatigue management web page https://www.uea.ac.uk/web/groups-and-centres/projects/fatigue-management-in-parkinson-s/refresh-study-getting-started. Participants will progress through the online resources at their own pace but are recommended to complete one module per week of information, and to participate in an exercise program at least three times per week. There are six modules (see Appendix 1 for more detail)

Participants will be tracked in their use of the online resources and defined as completing the fatigue management if they accessed at least four of the six modules.

## Control group

Participants in the control arm were waitlisted for 4 months to access the online fatigue management program. They received usual care for their Parkinson's, i.e., patients will attend consultant and nurse specialist appointments as scheduled based on their clinical needs. No additional contact or information regarding fatigue management will be provided.

## Blinding

Blinding to group allocation will not be possible as participants will know whether they had access to the online fatigue management program. All assessments will be completed by participants via online surveys. The trial data will be analysed by SA who will not be blinded to allocation.

## Sample size

The sample size of feasibility and pilot studies is generally influenced by the need to confidently estimate outcome parameters, such as standard deviation, for use in the sample size calculation of a definitive trial. According to Lancaster, Dodd, and Williamson (2004), a sample size of 30 is often considered a good rule of thumb.

We will adhere to this guideline by recruiting 20 participants for each arm of the study, resulting in a total of 40 participants. This sample size will allow us to collect sufficient data to estimate outcome parameters effectively and inform the design of future definitive trials.

#### Baseline measures

#### Demographic and Clinical Information.

Participants will be asked questions about demographic variables (e.g., age, gender, and ethnicity) informed by the Daisy guidance (EDIS 2022). We will also ask about their Parkinson's and its treatment (e.g., time since diagnosis, disease severity, comorbidities, medication regime) and identify baseline risks e.g., falls.). Levodopa equivalent dose will be calculated (Nyholm, D., & Jost, W. H. (2021).

#### Outcomes

Assessments will take place at baseline and 12 weeks after randomisation.

We anticipate that the ReFresh program will improve fatigue. In this pilot RCT we will use two measures of fatigue; the Parkinson's Fatigue Scale (PFS) (Baghoori 2017) and the Modified Fatigue Impact Scale (MFIS) (Fisk et al., 1994). These two measures assess related but not identical concepts. The PFS focusses on the experience of fatigue with some items that examine its impact on activities. Whereas the MFIS focusses far more on the impact having fatigue has on physical, social, and cognitive activities. We are unsure whether the ReFresh program will just impact on the sense of fatigue, or whether it will impact on participant's activity levels, so we will use both measures to determine which is most sensitive to any changes caused by the ReFresh program. MFIS is commonly used in fatigue research, and so these results could be more easily compared against other fatigue management protocols. The MFIS has excellent psychometric properties in multiple sclerosis populations; with internal consistency, Cronbach  $\alpha$  of 0.92 (Kos 2005), and a testretest reliability intraclass correlation coefficient (ICC) of 0.91, (Kos 2003). Although MFIS was not developed for Parkinson's it has been validated with this patient population; where it has high internal consistency, Chronbachs  $\alpha$ =0.96 (Schiehser 2012). However, the PFS was specifically developed and validated in people with Parkinson's (Baghoori 2017) and may therefore be more sensitive to disease specific factors. It is also a robust measure with a high internal consistency (Chronbach's  $\alpha$ =0.98) and good test-retest reliability Spearman R mean 0.63±0.06). The data from this pilot will allow us to refine the design of the planned

fully powered RCT to ensure its primary outcome uses the measure most likely to be sensitive to the changes possible from the ReFresh program.

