#### Method

#### Design

A pilot randomised controlled trial with **two parallel comparator groups**; the ReFresh online fatigue management program versus a wait list group who will receive treatment as usual, and then access the ReFresh online course at week 14 to ensure all end point data is gathered. We will recommend participants access one **module per week** i.e. six modules over six weeks, and undertake at **least three 30 minute sessions of exercise per week**. The primary outcome will be fatigue at 12 weeks. All measures will be unblinded as it is impossible to blind participants as to whether they have accessed the web site or not.

This pilot study will check study processes (e.g., recruitment, randomisation, treatment, follow-up assessments) all run smoothly, and determine the acceptability and practicality of the ReFresh intervention. It will also appraise the feasibility and sensitivity of two fatigue measures in order to decide which measure will be the primary outcome measure in the fully powered RCT this pilot study will inform. The fatigue measures are the Parkinson's Fatigue Scale (PFS) (Baghoori 2017) and the Modified Fatigue Impact Scale (MFIS) (Fisk et al., 1994). These will be measured at baseline and 12 weeks. Once the primary measure is selected it will inform the number of participants required for a fully powered RCT.

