## Aims

- To determine the size and variance of the difference in change in fatigue between
  the ReFresh group versus the waitlist group at 12 weeks. This will be used calculate
  the number of participants needed to fully power a randomised controlled trial to
  determine efficacy.
- To assess the feasibility, acceptability, and safety, of the ReFresh online fatigue management intervention.
- To assess the feasibility and acceptability of the design of the RCT protocol. In particular to determine which measure of fatigue to use as the primary outcome measure in the planned fully powered RCT.

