#### Randomisation and stratification

Upon completion of baseline data, participants will undergo randomisation to either the intervention arm (fatigue management) or the control arm (waitlist) utilizing the Sealed Envelope website. Sealed Envelope offers a robust online software application for randomising patients into clinical trials and capturing case report form data (EDC and ePRO).

The Simple randomisation service provided by Sealed Envelope will be employed for this trial. This uses a pseudo-randomisation number generator, and will allocate participants in a 1:1 ratio to ReFresh or wait list. To ensure a reasonably even distribution of patients in the 2 arms throughout the course of the trial, patients will be allocated in randomly permuted blocks of 4 and 6 (Sealed Envelope Ltd. 2022).

For the trial, a unique password will be assigned. Authorized personnel with the password will have the capability to conduct new randomisations. The results will be promptly displayed on-screen and emailed to both the trial administrator and the assigned individual overseeing the randomisation process, ensuring transparency and accountability.

Upon allocation participants will be sent an email informing them of their allocation. If allocated to the ReFresh group they will be sent the link to the ReFresh online program https://www.uea.ac.uk/web/groups-and-centres/projects/fatigue-management-in-parkinson-s/refresh-study-getting-started. If they are allocated to the waitlist group they will be told they will be contacted again in 12 weeks to complete the end point survey, and then at 16 weeks with the link to the ReFresh program (to ensure no contamination of the control group).

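### Ranking two fatigue scales by sensitivity with 20 per arm is imprecise unless they truly differ by about 0.2 SD, and sizing the definitive trial on the winner's observed effect biases that effect upward

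*Protocol*

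**What the plan says.** Both scales are listed as primary measures, taken at baseline and 12 weeks. Three places in the Protocol describe what happens next.

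- **Choice of scale.** Design says the pilot will "appraise the feasibility and sensitivity of two fatigue measures in order to decide which measure will be the primary outcome measure" of the later trial. Aims repeats the purpose: "In particular to determine which measure of fatigue to use as the primary outcome measure in the planned fully powered RCT". Outcomes treats sensitivity as something the pilot can establish: "so we will use both measures to determine which is most sensitive to any changes caused by the ReFresh program".
- **Use of the chosen scale.** Design continues: "Once the primary measure is selected it will inform the number of participants required for a fully powered RCT".
- **Use of the observed effect.** The first aim is to establish the "size and variance of the difference in change in fatigue between" the arms at 12 weeks, and to use it to calculate the definitive sample size.

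Sample size sets the pilot at "recruiting 20 participants for each arm of the study, resulting in a total of 40 participants", on the ground that "a sample size of 30 is often considered a good rule of thumb". The parameter it names for estimation is the standard deviation. Efficacy Analyses concedes that the study is too small for an accurate assessment of efficacy.

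**The concern.** Taken together, these statements describe two linked steps: rank the scales partly on the response seen in 40 people, then size the next trial on an observed difference. Each step has a weakness.

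First, ranking two treatment effects requires a precise estimate of the difference between them. The pilot was not sized for that comparison, so the less sensitive scale may be chosen.

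Second, the larger of two noisy estimates tends to be too large. If it becomes the planning effect, the definitive trial will on average be planned too small and will fall short of its intended power. The protocol states no safeguard against this, and the first aim as written leads to it.

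**Working it through.** **Inputs from the Protocol.** 20 per arm (Sample size); 1:1 allocation (Randomisation and stratification); t test on mean change (Efficacy Analyses). The size of 40 comes from a rule of thumb, so there is no calculation to reproduce beyond 20 + 20 = 40.

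**Assumptions, because the Protocol gives no figure.** A true standardised effect of 0.4 SD on the less sensitive scale; a true gap g of 0, 0.1 or 0.2 SD in favour of the other; a correlation r of 0.5 to 0.9 between the two changes; no dropout.

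**Step 1: precision of one effect.** SE = √(2/20) = 0.316 SD, so the 95% half-width is 1.96 × 0.316 = 0.62 SD.

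**Step 2: precision of the ranking.** The SD of the difference between the two observed effects is s = 0.316 × √(2(1 − r)). This gives 0.316, 0.245 and 0.141 at r = 0.5, 0.7 and 0.9. The chance of picking the truly better scale is Φ(g/s). At g = 0.1 and r = 0.7 this is Φ(0.1/0.245) = 66%. An 80% chance needs g = 0.842 × s, which is 0.27, 0.21 and 0.12 SD at the three correlations.

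**Step 3: inflation of the selected effect.** The mean excess over the larger true effect is s·φ(g/s) − g·Φ(−g/s). With g = 0 this is 0.399 × s: 0.13, 0.10 and 0.06 SD. At g = 0.1 it is 0.08, 0.06 and 0.02 SD.

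**Step 4: check by simulation.** At least 50,000 pilots per setting were simulated, with bivariate normal changes and effects standardised on the pooled SD. The cut in planned size is 1 − (unselected mean effect on the better scale / mean selected effect)². For g = 0 and r = 0.7 it is 1 − (0.408/0.511)² = 36%.

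| True gap (SD) | Better scale picked, r = 0.5 / 0.7 / 0.9 | Cut in planned size, r = 0.5 / 0.7 / 0.9 |
|---|---|---|
| 0 | not applicable (equal) | 43% / 36% / 24% |
| 0.1 | 62% / 65% / 75% | 27% / 20% / 8% |
| 0.2 | 73% / 78% / 91% | 16% / 10% / 2% |

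The simulated chances are about a point below the formula in Step 2, because the pooled SD is itself estimated.

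**Step 5: consequence for the next trial.** Suppose the true effect is 0.5 SD on both scales, with 90% power and two-sided 5% (all assumed). The correct size is 85 per arm. Planning on the mean selected effect of 0.63, 0.60 or 0.56 SD (r = 0.5, 0.7, 0.9) gives 53, 58 or 68 per arm, with true power of about 73%, 77% or 83%.

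**The case against.** Several points on the other side stand and limit the claim.

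- **A reader might infer that the choice is close to a coin toss.** The documents do not support that. It is roughly so only if the true gap is about 0.1 SD or less, and the gap is unknown. Outcomes gives a reason to expect a real gap: one scale covers mainly the experience of fatigue, the other its impact on activities. At a gap of 0.2 SD the choice is right about 73–91% of the time.
- **The scales being related does not make matters worse.** For a fixed gap, a higher correlation makes the ranking more reliable and the inflation smaller.
- **A single figure such as a 36% cut in size would be misleading.** It belongs to equal sensitivity and r = 0.7. If the scales are equally sensitive, choosing either costs nothing; if one is better, so that a wrong choice matters, the inflation shrinks.
- **Sensitivity is not the only criterion.** Design also names feasibility, although it does not say how the two are weighed.
- **The inflation is modest beside the noise.** At most it is about 0.13 SD, against a standard error of 0.316 SD for any single effect. Carrying the last observation forward sets the change of those lost to follow-up to zero, which may offset part of it.
- **A detailed selection rule could sit in an analysis plan that is not shown.** That is fair, and a missing rule is not the point here. The point is what the Protocol does state: that the pilot can determine the more sensitive scale, and that the observed difference will size the next trial.

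**Conclusion.** The concern holds in limited form. As written, the Protocol chooses the definitive primary scale partly on response observed in 40 people and uses the observed difference to size the next trial. The ranking is imprecise unless the scales truly differ by about 0.2 SD or more, and carrying the winner's effect forward biases the planning effect upward. At r = 0.7, the 95% interval for the difference between the two observed effects is about ±0.5 SD (1.96 × 0.26, the simulated SD).

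The size depends on assumptions the Protocol does not supply. With 0.4 SD on the lesser scale and r from 0.5 to 0.9, selection cuts the planned size by 24–43% at no gap, 8–27% at 0.1 SD and 2–16% at 0.2 SD.

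A reader might also infer that the Protocol's own argument makes PFS the natural default. It does not. Outcomes cites disease specificity for PFS. For MFIS it cites comparability with other fatigue research, validation in Parkinson's and a test-retest coefficient of 0.91 against 0.63. Those two coefficients differ in type and population and do not settle the matter either way. Patient safety is not involved; what is affected is one of the pilot's main outputs.

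**What to change.** 1. **Design and Aims.** State that the definitive sample size will rest on a pre-stated important difference on the chosen scale, together with the pilot SD and its confidence interval. The SD is the parameter that Sample size says the pilot is meant to estimate. The selected scale's observed effect should be reported but not used for sizing.
2. **Aims and Outcomes.** Replace *determine* with *inform*. Report the difference between the two scales' standardised effects with a paired confidence interval. Base the choice mainly on feasibility, completeness, floor and ceiling effects and relevance, unless that interval clearly separates the scales.

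No default scale need be imposed. Fixing one and switching only when a 95% interval excludes zero would switch correctly about 5–8% of the time at a gap of 0.1 SD and 9–19% at 0.2 SD (r = 0.5 to 0.85). That would in effect settle the choice beforehand and defeat the third aim.

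The cost is wording in three sections and one extra paired interval; recruitment, assessments and the pilot's size do not change. The downside is less freedom to follow the larger observed effect, and the definitive trial may be larger.

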#### **Primary Measures**

## **Fatigue**

- a. *Modified Fatigue Impact Scale (MFIS):* 21 items that assess the impact of fatigue on cognitive, physical, and psychosocial functioning. The total score ranges from 0 to 84, with higher scores indicating greater impact of fatigue (Fisk et al., 1994).
- b. *Parkinson's Fatigue Scale (PFS):* 16 items that mostly measure the experience of fatigue (Baghoori 2017). The total score ranges from 0 to 80, with higher scores indicating greater levels of fatigue.

## Secondary measures

#### Parkinson's disease Questionnaire - 39:

Much research in Parkinson's has used the Parkinson's-specific quality of life scale PDQ-39 and have found it to be sensitive to a variety of treatments including therapeutic rehabilitation interventions (Fitzpatrick et al., 1997). It uses 39 items to assess eight dimensions of health: mobility, ADL, emotional wellbeing, stigma, social support, cognition, communication, and bodily discomfort.

## The Parkinson Anxiety Scale (PAS):

The PAS is a self-reported outcome measure designed to assess anxiety specifically in individuals with Parkinson's disease. This tool enables participants to express their anxiety-related concerns, focusing on their unique experiences. It emphasizes individualized goal setting, self-reflection, and awareness of anxiety symptoms. The PAS concentrates on the participant's perception of their anxiety and their satisfaction level, providing a more nuanced understanding of anxiety issues relevant to our study. This approach is particularly

suitable for evaluating subjective symptoms like anxiety in Parkinson's disease, enhancing sensitivity to participants' concerns.

Previous studies in Parkinson's disease have successfully utilized the PAS to explore anxiety aspects (Moraes-Ferreira, R et. al, 2020; Leentjens, A. F et al., 2014). The PAS demonstrated good convergent and divergent validity in Cohort 2, confirming its status as a reliable and valid anxiety measure for use in PD patients. It is easy and brief to administer and exhibits better clinometric properties than existing anxiety rating scales (Leentjens, A. F et al., 2014).

## THE GERIATRIC DEPRESSION SCALE-15 (GDS-15)

The GDS-15 is a self-reported outcome measure designed to assess depression in the geriatric population (Justo-Henriques, S, et al, 2023). In our context, it is customized to capture depression-related aspects in individuals with Parkinson's disease. The GDS-15 encourages focused goal setting, self-reflection, and awareness regarding depressive symptoms. It measures the participant's perception of their depression and their satisfaction level, providing a more personalized evaluation of depression issues. This approach is particularly beneficial for examining subjective symptoms like depression in Parkinson's disease.

Previous studies have successfully employed the GDS-15 in assessing depression in Parkinson's disease (Meara, J., et al, 1999; Conradsson, M., 2013). The GDS was found to have a 92% sensitivity and an 89% specificity when evaluated against diagnostic criteria. The validity and reliability of the tool have been supported through both clinical practice and research (YESAVAGE, J et al, 1982).

## Pittsburgh Sleep Quality Index (PSQI)

The PSQI is a well-established tool for evaluating sleep quality and disturbances over a one-month time interval. Consisting of 19 items, the PSQI covers various aspects of sleep, and its total score indicates overall sleep quality (Zhong, Q. Y et al, 2015; Buysse, D. J. et al,, 1989). Previous studies in Parkinson's populations have demonstrated the validity and reliability of the PSQI, as evidenced by Wang, L., et al, (2022). The reliability and validity research on PSQI

are mainly based on the classical test theory (CTT). In most studies, Cronbach's  $\alpha$  fluctuated between 0.70 and 0.85. No studies reported Cronbach's  $\alpha$  above 0.9.

## The Multiple Sclerosis-Fatigue Self— Efficacy (MS-FSE) scale:

The MS-FSE Scale is a self-reported outcome measure designed to assess self-efficacy in managing fatigue, specifically in individuals with Multiple Sclerosis. In our study, it is adapted to evaluate self-efficacy in managing fatigue in individuals with Parkinson's disease. The MS-FSE Scale encourages focused goal setting, self-reflection, and awareness regarding self-efficacy in managing fatigue. It concentrates on the participant's perception of their ability to manage fatigue, providing a more individualized evaluation of self-efficacy issues. This approach is particularly relevant for investigating subjective symptoms like fatigue in Parkinson's disease (Thomas, S et al, 2014).

The MS-FSE scale measures an individual's self-efficacy in managing fatigue related to multiple sclerosis. With 9 items and a higher total score signifies greater self-efficacy in fatigue management. At a scale level, the Multiple Sclerosis-Fatigue Self-Efficacy scale is internally valid and has good sensitivity to change (Thomas, S et al, 2015).

## Canadian Occupational Performance Measure (COPM)

The COPM is a self-reported outcome measure that will be used by the ReFresh group only. This tool enables the client to identify what is meaningful for them to work on — in this context we will focus on fatigue-related goals. It encourages focussed goal setting, self-reflection, and awareness. It focuses on a person's perception of their performance and how satisfied they are with it, rather than measuring improvement in function. For a symptom as subjective as fatigue this may be a more sensitive way to measure fatigue-associated issues of importance to our participants. It is highly individualised as it focusses on the patient's personal goals. It has been used in Parkinson's disease (Gaudet 2002; Alsaeed 2021).

#### Adherence

We will track the completion of each module of the online ReFresh program by tracking access online web page hits, documents downloaded or requested in hard copy, exercise / activity / fatigue diaries.

## **Acceptability**

Self-reported feedback will be collected from ReFresh participants immediately after the completion of each online session via a brief evaluation questionnaire online. Using 5-point scales the items will include programme content (1 'not very relevant', 5 'very relevant'), format (1 'did not work at all', 5 'worked well'), usefulness (1 'not at all useful', 5 'very useful'), pace (1 'too slow', 5 'too fast') and duration (1 'too short', 5 'too long'). They will also be provided with an open response text box to make any further comments on the acceptability of the program.

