#### **Efficacy Analyses**

As this is a pilot RCT an accurate assessment of the efficacy of the intervention cannot be determined as the study is insufficiently powered. However, we will analyse the primary outcome measure at 12 weeks using the parametric student-t test for comparing mean change between the two intervention groups.

Intention to Treat (ITT) analyses will be performed for all outcomes and will comprise of all patients who had been randomised. For the intervention group, this was irrespective of their compliance with the ReFresh program. The principle of ITT was adopted as it provides a pragmatic estimate of the benefit of a change in treatment policy compared to the potential benefit in patients who receive treatment exactly as planned. As the ReFresh program was planned for delivery over a six-week period, some participants may not have received all the planned sessions. As this is more likely to reflect usual practice, primary analyses of all outcomes were conducted according to the ITT principle. Per Protocol (PP) analyses was planned for participants who had not deviated from the ReFresh protocol in such a manner that the assessment of efficacy could be biased. This was defined as patients accessing at least four out of six ReFresh modules. Imputation of missing/incomplete data is planned to use last observation carried forward method for all outcome measures.

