## 6. Recapping and taking the programme forward

Revisiting expectations; introducing the 'forcefield'; group activity to revisit themes of the programme; rationale of 'Keeping on Track' planner.

Promotion of exercise (see below for details of exercise program). This will be promoted within every module of the ReFresh Program.

Assessment of acceptability (see outcomes)

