#### Link

We will be in touch with you in 12 weeks to provide you with the endpoint survey link and further instructions. Completing the surveys requested is critically important to allow us to properly assess the ReFresh program.

Should you have any questions or require further assistance, please do not hesitate to contact us.

Best regards,

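### Acceptability is rated only on completing a session, so participants who complete none give no rating, those who stop neither rate the module they left nor say why, and later ratings come from an increasingly selected group

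*Protocol*

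**What the plan says.** The Aims section lists, among the pilot's purposes, "To assess the feasibility, acceptability, and safety, of the ReFresh online fatigue management intervention". The Acceptability section gives the means: "Self-reported feedback will be collected from ReFresh participants immediately after the completion of each online session", using a brief online form with 5-point items on content, format, usefulness, pace and duration. Free text belongs to the same form: "They will also be provided with an open response text box to make any further comments on the acceptability of the program". Appendix 1 places the assessment inside the programme. The description of each of the six modules closes with the line "Assessment of acceptability (see outcomes", which points back to the outcomes section.

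Two other parts of the protocol bear on people who stop. The Adherence section says "We will track the completion of each module of the online ReFresh program by tracking access online web page hits", along with downloads and diaries. The Intervention group section counts a participant as having completed fatigue management once at least four of the six modules were accessed. The Efficacy Analyses section expects incomplete uptake, noting that "some participants may not have received all the planned sessions".

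At week 12 the ReFresh arm is contacted in any case. The allocation email in Appendix 2 tells them: "We will be in touch with you in 12 weeks to provide you with the endpoint survey link and further instructions". No acceptability item, exit form, interview or question on reasons for stopping is described for that survey or anywhere else.

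**The concern.** The rating form follows completion of a session, so whether a rating exists depends on something closely tied to what is being rated. A self-guided online programme that someone finds irrelevant, badly formatted or too demanding is easily abandoned, and abandoning it means the next form is never reached.

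At stake is a stated aim. A pilot that is to inform a definitive trial needs to know why people disengage, and the protocol gives no set place for that answer. The gap lies in data collection. A statistical analysis plan could govern how ratings are summarised, but it could not recover opinions that were never asked for.

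**Working it through.** **Who can rate what.** Setting the Acceptability, Appendix 1 and Adherence sections side by side:

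| Participant | Ratings given | Not collected |
|---|---|---|
| Completes no module | none | any opinion; reason for not starting or not finishing |
| Completes modules 1 to k, then stops | modules 1 to k, with free text | rating of the module left; reason for stopping |
| Completes all six | all six | nothing |

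Tracking covers the whole ReFresh arm and shows where use ended. It records use, not opinion or reason.

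Compliance is defined by access, while the form follows completion. A participant who accessed exactly four modules is therefore counted as having completed the programme but gives no rating of the other two.

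**How far selection could move the result.** The protocol states no figure for acceptability, so there is none to reproduce. The only input taken from it is the arm size: "recruiting 20 participants for each arm of the study, resulting in a total of 40 participants", so n = 20. Everything else below is assumed.

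*Illustration 1: stopping before any rating.* Let A be the number who truly find the programme acceptable, and s the number who do not and who stop before rating anything. If everyone else rates, the observed share is A / (n − s). With A = 12 (true share 12/20 = 60%):

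- s = 0: 12/20 = 60%
- s = 2: 12/18 = 67%
- s = 4: 12/16 = 75%
- s = 6: 12/14 = 86%
- s = 8: 12/12 = 100%

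If the true share is varied and half of the dissatisfied are lost, a true 50% is observed as 10/15 = 67%, and a true 80% as 16/18 = 89%.

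*Illustration 2: stopping module by module.* Keep A = 12 and let the other U = 8 each have a chance h of stopping before they complete each module. The satisfied 12 never stop. Expected raters at module m = 12 + 8(1 − h)^m, and the observed share is 12 divided by that number.

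| h | Module 1: raters, share | Module 6: raters, share | All ratings pooled | Expected number of the 8 who never rate (8h) |
|---|---|---|---|---|
| 0.1 | 19.2, 62.5% | 16.3, 74% | 68% | 0.8 |
| 0.2 | 18.4, 65% | 14.1, 85% | 75% | 1.6 |
| 0.3 | 17.6, 68% | 12.9, 93% | 81% | 2.4 |
| 0.4 | 16.8, 71% | 12.4, 97% | 86% | 3.2 |

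The second illustration fits the design better, because most people who stop will have rated something. The distortion is small at module 1 and grows with each module. Few people are wholly silent. What is lost is mainly the later ratings and the reasons.

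**The case against.** A reader might infer that people who find the programme unacceptable and stop never rate it, so that the aim is answered only by those who stayed to the end. The protocol does not support that. The form follows every module from the first, so someone who leaves after module 2 has had two occasions to give low scores and to comment on the programme as a whole. Only those who complete no module are silent, which in the second illustration is 0.8 to 3.2 of 8. Tracking also shows non-starting and the point of drop-out across the whole arm, which is behavioural evidence on acceptability with all those randomised to ReFresh as its denominator. Both points stand, and they limit the finding.

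A reader might also infer that every item is biased upward. Pace and duration run from one undesirable extreme to the other, so the middle is best and upward has no favourable meaning. The direction is clear only for content, format and usefulness.

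Nor is a mean over all 20 a sensible target for a single late module, because people who never opened it have no view of its content or pace. Those who used a module are the natural group to rate it. What has the whole arm as its denominator is the overall question of whether the programme was acceptable and, if it was dropped, why.

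It can be said, finally, that no stated progression rule or threshold depends on these ratings, so no stated decision would change. That is true and keeps the point modest. Acceptability is nonetheless an aim in its own right. The planned carrying forward of last observations for all outcome measures does not help: a non-starter has nothing to carry forward, and a rating of one module is not a rating of another.

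**Conclusion.** The point holds as a limited one about collection. Every acceptability rating depends on completing a session, no other route is described, and reasons for stopping are not asked for, although the protocol expects that some will stop.

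The size cannot be derived from the protocol, which gives no rate of non-completion. On the assumed values above, a true 60% would appear as 68% to 86% over pooled ratings and as 74% to 97% at module 6. These figures assume that dissatisfied people are the ones who stop, that satisfied people never stop, and that everyone who completes a session fills in the form. If stopping were unrelated to opinion, for example because of illness or lack of time, the ratings would be less precise but not flattering. The missing reasons would still be a loss, since nothing else collected would tell these cases apart. The change is worth making as a cheap improvement and does not put the trial's conduct in doubt.

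**What to change.** Keep the per-module forms as they are. Add to the existing 12-week survey, for everyone allocated to ReFresh:

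- a brief overall acceptability rating, with a did-not-use option;
- how far the participant got;
- the main reason for stopping or not starting.

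The Resource utilisation section already plans a self-report measure at week 12 only, so the format is not new to the survey.

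Report per-module ratings beside the numbers who opened, completed and rated each module. Report overall acceptability and reasons for stopping with all randomised to ReFresh as the denominator and non-responders shown. With full response among 20, the share in the illustration would be 12/20 = 60%, the assumed true value.

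The cost is a few extra items, a minor ethics notification, and some recall error, because the programme is recommended over six weeks and the question comes at week 12. People who do not answer the 12-week survey would still be missed, so the change reduces the selection without removing it.
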